Appendix D: Clinic Variables Checklist

EXTRA-CVD

Clinic Variables Checklist

Date: _____

Study site (circle one): UH/SIU MetroHealth Duke

Instructions: For each of the following support services, please circle the option that best describes availability of that services in your ID or HIV clinic.

Resources	Not Available	Same Day Availability	Available by Advance Scheduling/Request Only
Adherence Support Services (Ex. Assisted pill box filling, DOTS, etc.)	0	1	2
CVD Prevention Specialist/Consultant with HIV Expertise	0	1	2
Dietician/Nutritionist	0	1	2
Exercise or Fitness Classes	0	1	2
Medication Adherence Incentive Programs	0	1	2
Nurse Support Line	0	1	2
Peer Coaching	0	1	2
Pharmacist	0	1	2
Social Worker Led Support Group(s)	0	1	2
Tobacco Cessation Program	0	1	2
Transportation Vouchers	0	1	2

What additional in-clinic resources are available to aid patients in managing their hypertension and/or hyperlipidemia?

Appendix E: PLHIV Pilot Participant Acceptability Testing Guide

Note: Not all questions will be asked explicitly. Participants may answer the questions, or cover the topic, in the course of the one-on-one conversation.

Study background

Welcome to our discussion! People living with HIV (PLHIV) are at increased risk for heart disease; however, the uptake of evidence based therapies to prevent heart disease is substandard. As such, strategies to improve the uptake of cardiovascular disease preventive therapies among PLHIVs are urgently needed. The goal of this study is to test a prevention, nurse-led intervention to extend the HIV/AIDS treatment cascade for the treatment of hypertension and high cholesterol among PLHIV on suppressive antiretroviral therapy.

Introduction

[Remind about Audio Recording and not to use real names]

Thank you for talking with me today. I am interested in learning more about your thoughts and beliefs about cardiovascular disease among your HIV+ patients. I am most interested in your thoughts about a new intervention our research team is planning on scaling-up at your clinic and for your HIV+ patients who have hypertension and high cholesterol. I am going to ask you some questions about these topics to hear about your experiences and perspectives. Please know that there is no right or wrong answer.

Here are the ground rules for our focus group discussion. We would like to have everyone participate in this discussion. I will only give you all a few probes and would like for you all to react to those probes. Beyond giving the probes, the discussion will be entirely driven by you all – my only job is to facilitate. And I will facilitate to get more clarity on statements you all share. Additionally, I am interested in engaging each of you to talk freely and to make sure everyone has equal opportunities to speak. My main purpose here is to ask questions, listen, and make sure that you have the opportunity to share your thoughts and perspectives. This session is being recorded, as was noted in the consent form you signed before, so that none of your informative comments and feedback will be missed. Again your names will not be collected and your comments will be confidential. Finally, you are under no obligation to talk about anything that you are not comfortable discussing with me. Do you have any questions or concerns before we begin?

[Facilitator, please note the participant's ID number in the audio recording so we can match it to the demographic information.]

Intervention Acceptability

Finally, we are interested in a new initiative, with a new nurse coordinator - led intervention, that we designed to help patients like you reduce their risk of heart disease in clinics around the

country. As such we would like to get your opinion on thoughts on this intervention. As a reminder, all information you provide will be confidential and aggregated across three clinics.

Facilitators and barriers to the nurse-led intervention for HIV+ patients with hypertension and high cholesterol

1. Please tell me your thoughts on working with your CVD nurse to tailor treatment for HIV+ patients like yourself who have either been diagnosed with hypertension and high cholesterol.
 - a. PROBE: What general experience do you have working with nurses to manage your health?
2. What do you think are some potential benefits or barriers of working with nurses?

[Interviewer will share the refined intervention structure and format with the participant(s).]

Thoughts on logistical factors (i.e. resources or tools at that clinic)

3. What are your initial thoughts on this intervention?
4. Do you like this intervention?
5. Please tell me any potential concerns you may have as an HIV+ patient participating in this intervention?
6. What are some potential benefits that you see with integrating this intervention into your current treatment?
7. What are some current resources or tools within your clinic that you think will help facilitate the integration of this intervention for your care?
 - a. Conversely, what may be some aspects of your clinic that you think will be a barrier to integrating this intervention for your care or treatment?
8. Do you feel that this intervention is relevant in terms of your health or the issues you are dealing with?
9. Would you be interested in having this service offered to you as part of your treatment?

Secondary/Follow-up Questions

Follow-up “Probes” after significant statements are made:

[Earlier/A moment ago/when you first started speaking/when you were talking about x] you said [significant statement].

- Can you tell me more about that?
- Can you tell me more about how that affects [X]
- Can you clarify what you mean by [significant statement]
- Can you give me an example of a time when [significant statement] happened to you

Conclusion

Is there anything else you want us to know about [X]? (YES return to interview; NO proceed)

We want to thank you so much for your participation and remind you that everything we have discussed will remain private. The audio file will be destroyed once this interview is transcribed, and the transcription will not contain your name or any identifying information.

Appendix F: PLHIV Pilot Participant Feasibility Testing Guide

Note: Not all questions will be asked explicitly. Participants may answer the questions, or cover the topic, in the course of the one-on-one conversation.

Study background

Welcome to our discussion! People living with HIV (PLHIV) are at increased risk of heart disease; however, the use of the most effective treatment options or approaches to manage heart disease in this population is not the best. As such, strategies to improve the uptake of heart disease prevention among PLHIVs is very important and needed in HIV clinics. The goal of this study is to test a prevention, nurse-led intervention to extend the HIV/AIDS treatment cascade for the treatment of hypertension and high cholesterol among PLHIV on suppressive antiretroviral therapy.

Introduction

[Remind about Audio Recording and not to use real names]

Thank you for talking with me today. I am interested in learning more about your thoughts and beliefs about cardiovascular disease among your HIV+ patients. I am most interested in your thoughts about a new intervention our research team is planning on scaling-up at your clinic and for your HIV+ patients who have hypertension and high cholesterol. I am going to ask you some questions about these topics to hear about your experiences and perspectives. Please know that there is no right or wrong answer.

Here are the ground rules for our focus group discussion. We would like to have everyone participate in this discussion. I will only give you all a few probes and would like for you all to react to those probes. Beyond giving the probes, the discussion will be entirely driven by you all – my only job is to facilitate. And I will facilitate to get more clarity on statements you all share. Additionally, I am interested in engaging each of you to talk freely and to make sure everyone has equal opportunities to speak. My main purpose here is to ask questions, listen, and make sure that you have the opportunity to share your thoughts and perspectives. This session is being recorded, as was noted in the consent form you signed before, so that none of your informative comments and feedback will be missed. Again your names will not be collected and your comments will be confidential. Finally, you are under no obligation to talk about anything that you are not comfortable discussing with me. Do you have any questions or concerns before we begin?

[Facilitator, please note the participant's ID number in the audio recording so we can match it to the demographic information.]

Intervention Feasibility

Protocol

We are interested in your experience and thoughts have participated in the pilot test for the new nurse coordinator-led intervention that we designed to help your patients reduce their risk of heart disease in clinics around the country. As a reminder, all information you provide will be confidential and aggregated across three clinics.

Participating in the nurse-led intervention for HIV+ patients with hypertension and high cholesterol:

1. Please tell me what your general thoughts and experience was with the nurse-led intervention?
2. What effect (positive or otherwise) did the intervention have on how you engaged with the following providers:
 - a. Prevention nurse: How did your interactions with the nurse evolve over the course of the 6-week pilot?
 - b. Your primary HIV nurse: Did your participation in this pilot affect your relationship with your primary HIV nurse? If so, how?
 - c. Your physician providers: How did your participation in this pilot affect your relationship with your primary HIV doctor and/or your primary care doctor?
3. After meeting with your nurse during the intervention what differences did you notice in how you responded to your own treatment?
 - a. PROBE: How were you better able to treat or care for your hypertension and cholesterol?

Thoughts on intervention's feasibility

4. How do you feel this intervention fits within your clinic setting?
5. After completing all of the intervention-related meetings with the nurse, what barriers did you feel that they faced in helping you manage your hypertension and cholesterol?
6. In what ways do you think this intervention, in its current form, will be an effective tool or resource for your clinic to integrate going forward?
7. In what ways do you think this intervention, in its current form, will NOT be an effective tool or resource for your clinic to integrate going forward?
8. What feedback have you shared or provided about the intervention with the clinic supervisors or nurses?
9. Does this intervention seem possible as a form of HIV treatment or management for people with hypertension and high cholesterol?
10. How do you think this intervention can be implemented within general HIV care clinics?

Secondary/Follow-up Questions

Follow-up "Probes" after significant statements are made:

[Earlier/A moment ago/when you first started speaking/when you were talking about x] you said [significant statement].

- Can you tell me more about that?
- Can you tell me more about how that affects [X]
- Can you clarify what you mean by [significant statement]
- Can you give me an example of a time when [significant statement] happened to you

Conclusion

Is there anything else you want us to know about [X]? (YES return to interview; NO proceed)

We want to thank you so much for your participation and remind you that everything we have discussed will remain private. The audio file will be destroyed once this interview is transcribed, and the transcription will not contain your name or any identifying information.

Appendix G: Health Worker Feasibility Testing Guide

Note: Not all questions will be asked explicitly. Participants may answer the questions, or cover the topic, in the course of the one-on-one conversation.

Study background

Welcome to our discussion! People living with HIV (PLHIV) are at increased risk for heart disease; however, the uptake of evidence based therapies to prevent heart disease is substandard. As such, strategies to improve the uptake of cardiovascular disease preventive therapies among PLHIVs are urgently needed. The goal of this study is to test a prevention, nurse-led intervention to extend the HIV/AIDS treatment cascade for the treatment of hypertension and high cholesterol among PLHIV on suppressive antiretroviral therapy.

Introduction

[Remind about Audio Recording and not to use real names]

Thank you for talking with me today. I am interested in learning more about your thoughts and beliefs about cardiovascular disease among your HIV+ patients. I am most interested in your thoughts about a new intervention our research team is planning on scaling-up at your clinic and for your HIV+ patients who either have or are at risk for CVD. I am going to ask you some questions about these topics to hear about your experiences and perspectives. Please know that there is no right or wrong answer.

Here are the ground rules for this semi-structured interview. I am going to ask you a few questions and will only give you a few probes with the intention that you will react to those probes. Beyond giving the probes, the discussion will be entirely driven by your responses – my only job is to facilitate. And I will facilitate to get more clarity on statements you share.

Additionally, I am interested in engaging each you to talk freely and to make sure you are able to share your thoughts fully. My main purpose here is to ask questions, listen, and make sure that you have the opportunity to share your thoughts and perspectives. This session is being recorded, as was noted in the consent form you signed before, so that none of your informative comments and feedback will be missed. Again your name will not be collected and your comments will be confidential. Finally, you are under no obligation to talk about anything that you are not comfortable discussing with me. Do you have any questions or concerns before we begin?

[Facilitator, please note the participant's ID number in the audio recording so we can match it to the demographic information.]

Intervention Feasibility

We are interested your experience and thoughts have participated in the pilot test for the new nurse coordinator-led intervention that we designed to help your patients reduce their risk of heart disease in clinics around the country. As a reminder, all information you provide will be confidential and aggregated across three clinics.

Participating in the nurse-led intervention for HIV+ patients with hypertension and cholesterol

1. Please tell me about your thoughts and experience with the nurse-led intervention?
2. How did the intervention impact (positive or otherwise) the way in which you engaged with HIV+ patients?

3. Did you feel prepared to integrate the intervention in your current treatment routine? If so, how? If not, what would have helped you to be more prepared?
4. After meeting with your patients during the intervention, what were some differences you noticed in how patients responded to their treatment?
 - a. PROBE: How were patients better able to treat or care for their CVD risks?

Thoughts on the intervention's feasibility

5. How do you feel this intervention fits within your clinic setting?
6. After completing all of the intervention procedures with your patients, did you feel that they still faced any barriers to managing their hypertension and cholesterol?
7. How did this intervention impact your workload with treating HIV+ patients?
8. In what ways do you think this intervention, in its current form, will be an effective tool or resource for your clinic to integrate going forward? In other words, what worked well in this intervention in this particular setting?
9. In what ways do you think this intervention, in its current form, will NOT be an effective tool or resource for your clinic to integrate going forward? Or what can be improved?
10. What feedback have you shared or provided about the intervention with your clinic colleagues?
11. Does this intervention seem possible as a form of HIV treatment or management for people with hypertension and high cholesterol?
12. How do you think this intervention can be implemented within general HIV care clinics?

Secondary/Follow-up Questions

Follow-up "Probes" after significant statements are made:

[Earlier/A moment ago/when you first started speaking/when you were talking about x] you said [significant statement].

- Can you tell me more about that?
- Can you tell me more about how that affects [X]
- Can you clarify what you mean by [significant statement]
- Can you give me an example of a time when [significant statement] happened to you

Conclusion

Is there anything else you want us to know about [X]? (YES return to interview; NO proceed)
We want to thank you so much for your participation and remind you that everything we have discussed will remain private. The audio file will be destroyed once this interview is transcribed, and the transcription will not contain your name or any identifying information.

Appendix H: Design Team Discussion Guide

Themes to be assessed:

- Previous design team experience.
- Understanding of the design team approach.
- Thoughts on the design team process for the nurse-led intervention.
- Experience for each phase or meeting of the design approach.
- Thoughts on the final intervention model.

General focus group discussion introduction:

For this part of our design team meeting, I am most interested in learning more about your thoughts and beliefs about the human-centered design process. I am going to ask you some questions about the process to hear about your experiences and perspectives. Please know that there is no right or wrong answer.

Here are the ground rules for our focus group discussion. We would like to have everyone participate in this discussion. I will only give you all a few probes and would like for you all to react to those probes. Beyond giving the probes, the discussion will be entirely driven by you all – my only job is to facilitate. And I will facilitate to get more clarity on statements you all share. Additionally, I am interested in engaging each of you to talk freely and to make sure everyone has equal opportunities to speak. My main purpose here is to ask questions, listen, and make sure that you have the opportunity to share your thoughts and perspectives. This session is being recorded, as was noted in the consent form you signed before, so that none of your informative comments and feedback will be missed. Again your names will not be collected and your comments will be kept confidential, not to be revealed to anyone outside of this room. Finally, you are under no obligation to talk about anything that you are not comfortable discussing with me. Do you have any questions or concerns before we begin?

Focus group questions

- What impact do you think your individual participation in the design team had on the final intervention model?
- Tell me about your experiences working on a team with individuals from different professions and roles?
- What was your personal contribution and the overall team's contribution to the design team?
- Was there a particular design phase (i.e. brainstorming, conceptualization, creation, iteration I, or iteration II) that you found to be most insightful for the entire design experience? Why or why not?
- Which design phase (i.e. brainstorming, conceptualization, creation, iteration I, or iteration II) did you find to be most challenging and why do you think so?
- Which design phase (i.e. brainstorming, conceptualization, creation, iteration I, or iteration II) did you find to be least challenging and why do you think so?

- What are your general thoughts on the final intervention model? Do you think that this version will meet the intended goals of our design team and that of the research study?
- Are there any closing thoughts that you want to share or that you think we should have discussed in terms of the final intervention model that we do not touch on?
- Are there any final thoughts that you want to share or that you think we should have discussed in terms of the design team experience that we do not touch on?

Thank you for your time and participation. We very much appreciate your comments, discussions, and input throughout the design process.

Appendix I: Trust and Communication Survey (PLHIV participant – Provider)

As a participant in the EXTRA-CVD study, we are asking you to complete a survey about your relationship with your healthcare providers. You will need at least 15 minutes of uninterrupted time to take this survey. If you have any questions, please see your EXTRA-CVD nurse or study coordinator. Please understand that your answers will be confidential. More specifically, your name and the names of your providers will never be recorded with your data. The unique ID numbers will be kept separately by study staff at your site who do not have access to the survey results. Please respond below in order to proceed:

- Yes I understand my rights as a participant in this study. I consent to proceed.
- No I do not consent and will not participate in this study and survey

Please enter here your unique participant ID. EXTRA-CVD study staff will ensure that you enter your correct ID. PLEASE DO NOT LIST YOUR NAME.

Please select which visit you completed today as part of this study. EXTRA-CVD study staff will ensure that you select the correct answer.

- Baseline visit
- 4 months visit
- 8 months visit
- 12 months visit

As a participant of this study, in the following sections, you will be asked some questions regarding your relationships with providers that may help treat your HIV or your blood pressure and cholesterol. At a minimum, this will include: your HIV provider and your EXTRA-CVD nurse.

Additionally, you may be asked some questions about the rest of your health care providers (for example, your Primary care physician, your HIV clinic nurse or you Non-HIV specialists).

Protocol

We hope to collect quality data for our research. But If you feel uncomfortable to answer any of the questions or feel that a question is not applicable to you, feel free to skip it.

Do you have a HIV clinic nurse?

Yes

No

Do you have a Primary care physician?

Yes

No

Please indicate which of the following medical professionals primarily treats your blood pressure (if multiple physicians care equally for your blood pressure, please select all that apply):

My HIV provider

My HIV clinic nurse

My Primary care physician

My Non-HIV specialist, please specify the specialist type (i.e.; cardiologist, nephrologist, endocrinologist): _____

No one manages my blood pressure

Please indicate which of the following medical professionals primarily treats your cholesterol (if multiple physicians care equally for your cholesterol, please select all that apply):

My HIV provider

My HIV clinic nurse

My Primary care physician

The same Non-HIV specialist who also treats my blood cholesterol (as indicated in the question above)

A different Non-HIV specialist from whom treats my blood cholesterol as indicated in the prior question), please then specify the specialist type- i.e. cardiologist, nephrologist, endocrinologist): _____

No one manages my cholesterol

*** The participant will complete the following survey items for each of their providers identified above.

Please think of your relationship with your [HIV, PCP, non-HIV specialist] provider. For the validity of this study, please answer honestly. Recall your answers are confidential and will never be shared with this provider nor anyone else outside our research team. Some of the questions may sound repetitive, please do read fully before answering each question.

How long have you been a patient of this provider?

- I just became a patient this past month
- Less than 6 months
- 6 months to 1 year
- 1-2 years
- 3-5 years
- More than 5 years

How often do you communicate with this provider?

- Every 1-2 months
- Every 3-4 months

Protocol

Every 5-6 months

Once yearly

Please rate the following statements based on your recent visits with this provider and overall care with this provider.

	Strongly Disagree	Disagree	Neither Agree nor Disagree	Agree	Strongly Agree
My provider has much knowledge about the treatment that needs to be done.					
My provider is very concerned about my welfare.					
I feel I can discuss with my provider how I honestly feel about my health treatment, even negative feelings and frustration.					
Overall, I trust my provider.					

	Strongly Disagree	Disagree	Neither Agree nor Disagree	Agree	Strongly Agree
My provider and I communicate effectively.					
My provider listens carefully to me.					
Overall, I am satisfied with the communication with my provider.					

Protocol

	Strongly Disagree	Disagree	Neither Agree nor Disagree	Agree	Strongly Agree
My provider and I have a good relationship.					
I feel part of a team with my provider in regards to my health care and needs.					
Overall, I like my provider.					
Overall, I am satisfied with my provider.					

Do you have any recommendations to improve your care experience with this provider?

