Frequency of contact: All subjects will complete the same assessments at the same time-points (in-office BPs, lipid profile, perceived ASCVD risk survey, and network analysis survey). The prevention nurse will then contact the intervention subjects at up to 2-week intervals as necessary to carry out the multi-component intervention. Frequency of contact will be determined according to protocol triggers that may be patient or prevention nurse initiated (e.g. home BP values are high, checking for side effects after starting a statin). At a minimum, the prevention nurse will have face-to-face meetings at 0, 4, 8, and 12 months, as well as a mid-period telephone call between in-person visits to “check-in” about home BP values and medication adherence. An initial 2-week follow-up call will ensure proper use of the home BP monitor and to address any other questions. Two example scenarios of relatively lower intensity and higher intensity intervention are shown in **Figure 3** with the education control group as a reference. As demonstrated by the figure, a strict attention control group is not appropriate since the dose of attention will vary according to the needs of the participant.

As with control patients above, study visits must be completed +/- 14 days from the calculated visit date. Visits done between 14 and 28 days after the calculated visit date will be considered a protocol deviation. Visits outside of the +28 day window will not be scheduled and that visit will be considered missing for that patient. The fasting lipid panel blood draw will be done at the time of study visit or within a +/- 10 day window. Study calls will be completed +/- 14 days of the scheduled due date. In the event that the study nurse has made no less than three

Protocol

attempts to schedule a participant's follow-up visit, a letter (Appendix R) will be sent to the participant.

[figure not shown]

Figure 3: Example scenarios of intervention participant contact frequency. (A) Participant with lower intensity requirements; (B) Participant with higher intensity requirement; (C) Control participant. Squares represent in-person visits and lines are telephone contact.

EXTRA-CVD Intervention components:

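### Appendix I survey: the cholesterol question's specialist options refer back to the wrong condition, and the contact-frequency scale has no option for contact more often than every 1-2 months or for no prior contact

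*Combined protocol and SAP*

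**What the plan says.** Appendix I first asks: "Please indicate which of the following medical professionals primarily treats your blood pressure". One answer is a non-HIV specialist, with the type to be written in. The next question reads "Please indicate which of the following medical professionals primarily treats your cholesterol", and two of its answers concern non-HIV specialists:

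- The 'same' option is worded "The same Non-HIV specialist who also treats my blood cholesterol (as indicated in the question above".
- The 'different' option, which goes on to request the specialist type, is worded "A different Non-HIV specialist from whom treats my blood cholesterol as indicated in the prior question".

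The instruction after these questions is "The participant will complete the following survey items for each of their providers identified above". The rating block then asks how often the participant communicates with the provider. The choices are "Every 1-2 months", two longer intervals (3-4 and 5-6 months) and once yearly.

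On who is covered, the survey introduction says "At a minimum, this will include: your HIV provider and your EXTRA-CVD nurse". On nurse contact, Aim 2 Procedures (Frequency of contact) says the nurse will "contact the intervention subjects at up to 2-week intervals as necessary". The home BP monitoring component plans calls every 2 weeks when BP is poorly controlled.

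Under PLHIV-Provider Trust & Communication Ties (Aim 3 Procedures), each provider has a unique identifier, which the nurse helps the participant enter. The main analysis there is the intervention effect on ties. Mediation of the BP and non-HDL effects by changes in ties is exploratory.

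**The concern.** Both specialist options in the cholesterol question depend on a back-reference, and both name cholesterol where the earlier question was about blood pressure. Neither option can therefore clarify the other. The answer helps to decide which specialists count as identified for rating, and the type of a separate cholesterol specialist is requested only under 'different'.

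The frequency scale raises a different issue. The protocol deliberately lets nurse contact vary with need, and its Figure 3 contrasts lower- and higher-intensity participants. A scale whose most frequent option is every one to two months cannot express fortnightly contact. It also has no answer for a relationship that begins on the day of the survey, although the survey is given at baseline and intervention participants meet the nurse at enrollment.

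At stake are the tie analysis in Aim 3 and the exploratory mediation analysis built on it.

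**Working it through.** The plan states no figure to reproduce. The first part is a reading of the text and the second a count of planned contacts.

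**Back-reference.** Read literally, 'same' means that the cholesterol specialist is the one who treats cholesterol, which is true of anyone who has one. 'Different' means that the cholesterol specialist is not the one who treats cholesterol, which is true of nobody. Three situations follow:

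| Participant's care | Intended answer | Literal answer | Effect |
|---|---|---|---|
| One specialist treats both conditions | Same | Same | None |
| Specialist X for BP, specialist Y for cholesterol | Different, type of Y recorded | Same | Field wrong, type of Y lost, Y may go unrated |
| No specialist for BP, specialist Y for cholesterol | Different, type of Y recorded | Same | Field wrong, type of Y lost, no earlier specialist to point to |

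The literal reading therefore errs in one direction: true 'different' answers become 'same'. How many participants would read it that way cannot be known from the documents.

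**Contact frequency.** The inputs are the contact schedules for the two arms in Aim 2 Procedures.

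- Intervention minimum over 12 months: 4 visits (0, 4, 8, 12 months) + 3 mid-period calls + one 2-week call = 8 contacts. 12 / 8 = one every 1.5 months. Without the early call, visits and calls alternate about every 2 months.
- Intervention ceiling: 52 weeks / 2 = about 26 contacts a year.
- Control: 4 visits at 4-month spacing.
- Top category: every 2 months to every month, or 12 / 2 = 6 to 12 / 1 = 12 contacts a year.

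The minimum of 8 lies inside the top category. The ceiling of 26 lies outside every category, at 26 / 12 = 2.2 times the most the top one describes. A participant contacted fortnightly must skip the item or choose the top category. A range of 26 / 8 = 3.25-fold then has one usable answer. Control contact every 4 months fits the second category, so at planned schedules the item still separates the arms. It does not separate intensities within the intervention arm.

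**Whether the item applies to the nurse.** The introduction says the nurse is covered. The rating stem names only the HIV provider, the PCP and the non-HIV specialist, and the identifying questions do not list the nurse as an answer. The two parts of Appendix I do not agree, so the frequency result is conditional.

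**The case against.** A reader might infer that provider identity and communication are mis-recorded. The documents do not support that. Identity comes from the unique identifier, so a specialist rated twice would show the same identifier twice. Communication has its own agreement-scale items (effectiveness, listening, satisfaction), which do not use the frequency categories. No section says that the frequency item enters a tie score.

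A reader might also infer that the item merely re-codes treatment arm. That could apply only to ratings of the nurse, and the stem leaves unclear whether she or he is rated. For other providers, nothing shows that the categories are too coarse.

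Other mitigations are real. Both options point to the preceding question, so many participants will guess the intent, and staff are available to help. Items may be skipped. The tenure item has an answer for a new relationship. The Component 2 process measures and the Aim 3 REDCap encounter forms record nurse telephone contact separately, and a composite dose measure is planned. About 26 contacts is a ceiling for contact made as needed, not an expected value.

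These arguments limit the consequences but do not remove the defects. Both specialist options name the wrong condition, the specialist's type can be lost, a second specialist can go unrated, and the frequency scale lacks options at both ends of the experience it is meant to cover. Help from staff reduces the risk but does not make the recorded answer interpretable.

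**Conclusion.** The point holds as a minor instrument defect with two parts. The wrong back-reference is certain from the text. It puts at risk the same/different field, the cholesterol specialist's type and, occasionally, the rating of a second specialist. The missing frequency options are also certain. Their consequence, that 8 and about 26 contacts a year cannot be told apart, rests on the nurse being rated on this item and on fortnightly participants choosing the nearest category.

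The effect is confined to the EXTRA-CVD Aim 3 tie analysis and the exploratory mediation analysis. How far the frequency item matters even there depends on whether it enters a tie score, which the plan does not say. The systolic BP and non-HDL treatment comparisons do not use the survey, and Aim 4 Procedures exclude it for AAIM-High participants.

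**What to change.** **Survey text.** In both specialist options of the cholesterol question, replace 'blood cholesterol' with 'blood pressure'. Add 'More than once a month' and 'No contact before today' to the frequency item. Reconcile the introduction with the rating stem on whether the nurse is rated.

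**Analysis.** State whether the frequency item enters the tie score. Carry a survey-version flag. For comparisons across versions, collapse the new top category into the existing one; 'No contact before today' has no counterpart in the older form and should be kept apart.

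**Completed surveys.** Settle same/different from the unique provider identifiers, not from specialist type, which is missing under 'same' and cannot distinguish two specialists of one type. A single specialist identifier does not prove that there was only one specialist, so such records may stay unresolved unless the nurse's care-team key settles them. An omitted rating cannot be recovered.

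**Nurse contact intensity.** Take it from the logged contact data (Component 1 and 2 process measures and the Aim 3 REDCap encounter forms), not from this item. Component 1 covers contact with providers, so participant contact comes mainly from the other two.

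**Cost.** A few words of survey text, a minor IRB modification, the version flag, and some loss of comparability between earlier and later visits, which collapsing the categories limits. If survey collection has already closed, only the analysis steps apply.
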